## 8. INTERIM ANALYSIS

There is no planned any interim analysis.

The optimal two stage Simon Model is carried out in two steps. The purposes of the step 1 analysis are to allow early stopping of the study for futility.

Following the two-stage Simon design, it will be reviewed whether if at least 4 of the first 12 evaluable patients show tumour response according to RECIST version 1.1, and if this occurs,

additional patients will be included to get a total of 34 patients. If 3 or less patients of the first 12 evaluable patients show an OR, recruitment will be stopped.

In case of recruitment is stopped after the step 1, it will be reviewed the feasibility and interest of performing some of the described secondary and exploratory analysis based on the available number of patients and samples.

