8.2.6. Efficacy Analyses

All efficacy definitions are described in section 6.1.

All efficacy analysis will be based on the Efficacy population. Additional efficacy analyses will be performed on the ITT population.

All primary and secondary endpoints based on radiological (and photographic where applicable) assessments of tumour burden (ORR, CBR, RD, PFS, etc.) will be derived using the local radiologist's/investigator's assessment.

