8.2.6.1. Analyses of Primary Endpoint

The primary endpoint is ORR

Objective Response Rate (ORR): A patient will be considered to have achieved an OR if the patient has a sustained complete response (CR) or partial response (PR) according to RECIST v.1.1 definitions. Otherwise, the patient will be considered as non-responders in the ORR analysis. ORR will be estimated by dividing the number of patients with objective response (CR or PR) by the Efficacy population ("response rate").

$$\text{Objective Response Rate} = \frac{\text{Number of CRs + PRs}}{\text{Efficacy population}}$$

The ORR will be reported, including a 95% confidence interval.

These analyses will be conducted at a two-sided 0.05 level of significance.

The number of responders needed at the end of stage 2 to reject the null hypothesis is at least 14 responders.

Additional sensitivity analyses will be outlined in the SAP. For the analysis in the ITT population, patients with inadequate data for tumour assessment (e.g., no baseline assessment or no follow-up assessments) will be considered as non-responders in the OR rate analysis.

In addition, the best objective response for each patient will be summarized.

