### 3.1 Sample Size

We have set the null hypothesis (H0) that ORR will be 30% (ORR achieved by TN patients treated with gemcitabine plus carboplatini) versus the alternative hypothesis (H1) that ORR will be 54% (ORR showed by TN *BRCA* mutated patients treated with olaparibii). Using an optimal two-stage Simon model and considering an alpha error of 0.05 and a statistical power of 80%, it will be required to include 31 evaluable patients. Twelve evaluable patients will be enrolled in the first

stage, and if at least 4 patients of them have response, additional patients will be recruited to get a total of 31 evaluable patients. Assuming a 10% dropout rate, the total number of patients to be enrolled is 34. Considering, these data the number of responders needed at the end of stage 2 to reject the null hypothesis is at least 14 responders.

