### **4.2 Efficacy population**

A subset of the ITT population that have received at least one dose of study medication and has performed at least one tumour response assessment according to RECIST version 1.1 (unless PD, death or unacceptable toxicity is observed before the first tumour response assessment) and without major protocol deviations according to the protocol deviation manual.

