### 9.2.1.1 Analyses of Primary Endpoint

The primary endpoint is ORR.

**Objective Response Rate (ORR):** A patient will be considered to have achieved an objective response (OR) if the patient has a complete response (CR) or partial response (PR) according to RECIST version 1.1 (4) definitions. Otherwise, the patient will be considered as non-responder in the ORR analysis. ORR will be estimated by dividing the number of patients with objective response (CR or PR) by the **Efficacy** population ("response rate").

$$\text{Objective Response Rate} = \frac{\text{Number of CRs + PRs}}{\text{Efficacy Population}}$$

The ORR will be reported, including a 95% confidence interval using the Clopper-Pearson method (5).

These analyses will be conducted at a two-sided 0.05 level of significance.

The number of responders needed at the end of stage 2 to reject the null hypothesis is at least 14 responders.

Additional sensitivity analyses will be done with the ITT population. For the analysis in the ITT population, patients with inadequate data for tumour assessment (e.g., no baseline assessment or no follow up assessments) will be considered as non-responders in the ORR analysis.

In addition, the best objective response (BOR) for each patient will be summarized.

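### The success count of 14 responders belongs to 31 evaluable patients, but accrual runs to 34 and no count is given for any other final number

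*SAP*

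**What the plan says.** SAP 3.1 and Protocol 8.1.1 set a null ORR of 30% against an alternative of 54%, with an optimal two-stage Simon design, alpha 0.05 and power 80%. Stage 1 has 12 evaluable patients. With at least 4 responders, "additional patients will be recruited to get a total of 31 evaluable patients". A 10% dropout allowance brings enrolment to 34, and the same paragraph requires at least 14 responders at the end.

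The operating sections use the other total. SAP 8 says that after a positive stage 1 "additional patients will be included to get a total of 34 patients"; Protocol 3.1.1 and 8.2.10 say the same.

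On the analysis set, Protocol 8.2.6 states that "All efficacy analysis will be based on the Efficacy population", and Protocol 8.2.6.1 that "ORR will be estimated by dividing the number of patients with objective response (CR or PR) by the Efficacy population". SAP 4.2 and Protocol 8.2.1 (Patient Populations) keep patients in this set if progression, death or unacceptable toxicity comes before the first assessment. They remove patients with no dose, no assessment or a major deviation; the set must be "without major protocol deviations according to the protocol deviation manual". It has no upper limit below the number enrolled.

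The decision rule is then repeated without a denominator: "The number of responders needed at the end of stage 2 to reject the null hypothesis is at least 14 responders".

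**The concern.** A two-stage critical count holds only for the final sample size it was derived for. Here the count is fixed and the sample size is not: the Efficacy population can be as large as 34 or can fall below 31.

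Above 31 the fixed count is too lenient. Success could be declared at 14/32 = 44% or 14/34 = 41%, against the intended 14/31 = 45%. Below 31 it is too strict, and power drops.

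The gap also leaves room for a choice made after the data are seen. The trial is single-arm, response is assessed locally, and membership of the Efficacy population depends partly on which deviations are called major. Moving the final n by one or two can change whether 14 responders is a valid success. The Clopper-Pearson interval and the ITT sensitivity analysis in SAP 9.2.1.1 are reported beside the count rule and do not alter the decision.

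**Working it through.** **Inputs.** p0 = 0.30, p1 = 0.54, n1 = 12, continue with 4 or more, 31 evaluable, success at 14 or more, 10% dropout, 34 enrolled (SAP 3.1, SAP 8; Protocol 8.1.1, 8.2.10).

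**Formula.** With stage-1 threshold *a*, final size *n* and success count *r*:

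P(reject | p) = Σ (x = a to 12) C(12,x) p^x (1−p)^(12−x) × P[Bin(n−12, p) ≥ r − x]

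At p0 this is the type I error; at p1 it is the power.

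**Reproducing the plan.** I searched for the design with the smallest expected sample size under p0, with one-sided alpha at most 0.05 and power at least 80%. The search returns n1 = 12, n = 31, success at 14 or more: alpha 4.28%, power 80.7%. One-sided 0.025 gives n = 37 and a count of 17 instead. So the plan's 12, 31 and 14 come from a one-sided 0.05 design, although the sample-size text does not state the sidedness. The optimum continues with **5** or more of 12, not the plan's 4 or more. That is a separate point, so both thresholds are shown. With 4 or more, 14/31 gives alpha 5.03% and power 86.1%.

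**Keeping 14 at other sizes.**

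| Final n | Alpha, 4+ of 12 (plan) | Power, 4+ | Alpha, 5+ of 12 | Power, 5+ |
|---|---|---|---|---|
| 28 | 2.03% | 72.5% | 1.87% | 69.7% |
| 29 | 2.84% | 78.0% | 2.54% | 74.3% |
| 30 | 3.83% | 82.5% | 3.35% | 78.0% |
| 31 | 5.03% | 86.1% | 4.28% | 80.7% |
| 32 | 6.44% | 88.9% | 5.33% | 82.8% |
| 33 | 8.04% | 90.9% | 6.48% | 84.3% |
| 34 | 9.83% | 92.4% | 7.71% | 85.3% |

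For example, at n = 34 the single-stage probability of 14 or more is 11.03%. The plan's stage-1 stop removes 1.20 points of that, leaving 9.83%.

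**How likely each size is.** Assume each of 34 patients is lost independently with probability 10%, so the number evaluable is Bin(34, 0.9) with mean 34 × 0.9 = 30.6.

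- P(n > 31) = 19.3% + 10.5% + 2.8% (for 32, 33, 34) = 32.6%
- P(n = 31) = 22.8%
- P(n < 31) = 44.6%

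The final n therefore differs from 31 with probability 32.6% + 44.6% = 77%.

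**Averages.** Given n > 31 and the plan's threshold: (0.193 × 6.44% + 0.105 × 8.04% + 0.028 × 9.83%) / 0.326 = 7.2%. With 5 or more it is 5.9%. Weighting alpha over all sizes gives 4.8% (4 or more) or 4.1% (5 or more).

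**Other loss rates (assumed).**

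| Loss | Average alpha, 4+ | Average alpha, 5+ |
|---|---|---|
| 5% | 7.1% | 5.7% |
| 8% | 5.7% | 4.7% |
| 10% | 4.8% | 4.1% |
| 12% | 4.1% | 3.5% |
| 15% | 3.1% | 2.7% |

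P(n > 31) is 76% at 5% loss and 48% at 8% loss.

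**The case against.** The two totals need not conflict: 31 is the evaluable target, 34 is that target with a dropout allowance, and the count of 14 first appears in the same paragraph as 31. On the plan's own 10% loss, average alpha is 4.8% and average power 83.5%, so the design meets its targets on average. The 9.8% figure needs no losses at all, which has probability 2.8%. Loss could also exceed 10%, because major deviations are excluded, and average alpha then falls. Part of the excess under the plan's stage-1 rule, including the 5.03% at n = 31, comes from the threshold of 4. Low power at 28 or 29 is mainly lost sample size, which no choice of count fully restores.

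All of this is correct and limits the size of the problem, but does not remove it. A recruitment target is not an analysis rule, and the analysis sections apply 14 to whatever size the Efficacy population has. Above 31, alpha exceeds 5% under either threshold, so correcting stage 1 alone does not cure it. The average depends on a loss rate that the sponsor does not control, and the decision will be taken at one realised n.

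**Conclusion.** The point holds. The rule as written is valid only if the Efficacy population has exactly the size for which 14 was derived, and neither document provides for another size. If more than 31 patients are evaluable, the stated 0.05 is exceeded: 6.4% to 9.8% with the plan's stage-1 rule, 5.3% to 7.7% with the Simon-optimal one. At 28 or 29 evaluable, power with the plan's rule is below the stated 80%.

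This should be corrected, but the excess is conditional: at 10% loss it arises in about a third of outcomes, and the overall average stays below 5%. The figures assume a one-sided 0.05 design, inferred because it reproduces 12, 31 and 14, and independent losses across all 34 patients.

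**What to change.** Amend SAP 9.2.1.1 and Protocol 8.2.6.1 before the final responses are known, and settle the stage-1 threshold in the same amendment.

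**Option A.** Base the reject decision on the first 31 evaluable patients in order of enrolment, and still report ORR and its interval in the whole Efficacy population. With a threshold of 5 or more at stage 1, alpha is 4.3% and power 80.7%. If 4 or more is kept, alpha is 5.03% and the SAP should say so. The counts below are still needed for n under 31.

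**Option B.** State the critical count for each attained n:

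| n | 5+ of 12: count (alpha, power) | 4+ of 12: count (alpha, power) |
|---|---|---|
| 27 | 13 (3.1%, 74.5%) | 13 (3.5%, 78.1%) |
| 28 | 13 (4.1%, 78.3%) | 13 (4.7%, 82.7%) |
| 29 | 14 (2.5%, 74.3%) | 14 (2.8%, 78.0%) |
| 30 | 14 (3.4%, 78.0%) | 14 (3.8%, 82.5%) |
| 31 | 14 (4.3%, 80.7%) | 15 (2.3%, 78.0%) |
| 32 | 15 (2.7%, 77.7%) | 15 (3.1%, 82.4%) |
| 33 | 15 (3.5%, 80.4%) | 15 (4.1%, 85.9%) |
| 34 | 15 (4.4%, 82.5%) | 16 (2.6%, 82.3%) |

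Below 27, a count of 13 still controls alpha but is conservative.

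**Cost.** One sentence or a short table, plus the protocol amendment that Protocol 8.2.1 (General Considerations) and SAP 1 require for major changes to the primary analysis; no extra patients. Option A leaves up to three evaluable patients out of the decision. Option B asks for one more responder above 31. With 4 or more kept, it asks for one more from n = 31 and two more at n = 34, and power at n = 31 falls from 86.1% to 78.0%. Some sizes stay below 80% power under either threshold.

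The sentence just before the count in both sections refers to a two-sided 0.05 level, which does not match the one-sided design: 14/31 has a Clopper-Pearson 95% lower limit of 27.3%, below 30%. Reconcile it in the same edit.

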## **8.1 Purpose of interim analysis**

Not applicable.

## **8.2 IDMC (Interim Data Monitoring Committee)**

Not applicable.

# **9. STATISTICAL METHODS ANNALYSES**

## **9.1 Statistical Methods**

For descriptive analyses, frequencies, percentages and ninety-five percent confidence intervals of interest will be calculated for categorical variables wherever possible. For continuous variables, standard descriptive statistics, such as total number of observations, number of available data, mean, standard deviation, minimum, percentile 25, median, percentile 75 and maximum will be calculated.

For efficacy analyses the 2-sided 95% confidence interval will be presented wherever possible. A bilateral (2-sided) 5% significance level will be used to assess the statistical significance.

Chi-square  $\chi^2$  test or Fisher exact test will be used to explore the relationship between two qualitative variables. Mann-Whitney-Wilcoxon test will be used to compare a quantitative variable in two independent groups.

Logistic regression models will be used to test the association of co-variables with a binary variable (ORR, CBR) and to estimate odds ratios and their 95% confidence intervals.

Kaplan-Meier Method will be used to estimate the survival function, survival median and probabilities of occurrence of event at a certain point of time.

Cox Proportional Hazards Regression Model will be used to estimate the hazard ratio and assess the association between several risk factors, considered simultaneously, and survival time (PFS, RD, OS).

## 9.2 Statistical analyses

An exploratory and descriptive analysis will be developed for each variable in the study. All continuous variables will be summarized using the following descriptive statistics: n, mean, median, standard deviation, maximum and minimum and confidence interval (CI) will be performed when this information is considered relevant to describe a unique variable. The frequency and percentages of observed levels will be reported for all categorical measures. Ninety-five percent confidence intervals will be provided for estimates of interest wherever possible.

All statistical tests will be performed with a significance level of 5%, unless otherwise specified. For qualitative comparison of independent samples the Chi-squared test (or Fisher's exact test for 2x2 tables) will be used, while for the quantitative samples Mann-Whitney-U will be used. Logistic regression models will be used to test the association of covariables with objective response (yes/no) and clinical benefit (yes/no), and to estimate odds ratios and their 95% confidence intervals. The Kaplan-Meier limit-product method will be used to estimate PFS and OS. The Kaplan-Meier survival curve will be presented graphically. Median PFS and OS with the 95% confidence interval will be reported. Cox regression models will be used to estimate hazard ratios and its 95% confidence interval. The Wald test will be used to establish the prognostic importance of each covariable.

All efficacy analyses will be based on the **Efficacy** population. Additional efficacy analyses will be performed on the ITT population.

All primary and secondary endpoints based on radiological (and photographic where applicable) assessments of tumor burden (PFS, ORR, CBR and RD) will be derived using the local radiologist's/investigator's assessment.

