**Overall Survival (OS):** OS is defined as the time from the date of study enrolment to the date of death from any cause. OS data will be censored on the last date the patient is known to be alive.

OS will be analysed in the ITT and Efficacy population. The median event times and 95% CIs will be estimated.

All of the above secondary analyses will be conducted at a two-sided 0.05 level of significance.

The secondary time-to-event endpoints (RD, PFS, OS) will be summarised using a Kaplan-Meier analysis and associated curves.

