### **9.2.3      *BRCA1/2* Methylation and expression analysis**

**To explore changes in the methylation status of *BRCA1/2* promoter in germline DNA prior and after treatment discontinuation.**

The methylation status of the *BRCA1* and *2* promoters will be measured in germline DNA from blood cells collected at the beginning of the study and after disease progression or at the end of study treatment for other cause, and in paired primary and metastatic lesions. Methylation status will be provided as a continuous (the methylation value will be obtained from the average of the CpG dinucleotides included in the sequence analysed) and also as a binomial variable (status methylated or not methylated).

If methylation status is a continuous variable, to compare the value of methylation between prior and after treatment, the difference of these values will be used and will be used statistical t (student-Fisher) or Wilcoxon test depending if it must be used a parametric or non-parametric test.

If methylation status is a binomial variable, to compare the value of methylation between prior and after treatment it will be used the McNemar test or exact binomial test.

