#### **To correlate *BRCA1/2* expression with efficacy parameters:**

mRNA levels of *BRCA1* and *2* will be assessed in blood and available tumour samples. Expression data will be given as a continuous or as a binomial variable.

To evaluate the effect of *BRCA1/2* expression with time to event variables (PFS, OS) it will be used a univariate Cox Regression model.

To evaluate the effect of *BRCA1/2* expression with efficacy rate parameters it will be used chi-square test if both of them are quantitative, and will be used an ANOVA analysis if one variable is quantitative and the other one are qualitative.

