#### **9.2.4 Other Analyses**

##### **9.2.4.1 Biomarker Exploratory Analyses**

The biomarker analyses of the present study will be exploratory and primarily make use of descriptive statistical methods. For continuous variables, descriptive statistics including the mean, standard deviation, median, minimum and maximum values will be provided. Categorical variables will be summarized by numbers and proportions (if possible, the 95% confidence intervals will be calculated).

Appropriate statistical methods will be used to investigate any possible relationship of biological subtypes/profiles and biomarker levels with the efficacy end-points and outcome, and to compare with data from healthy volunteers (if available). Any exploratory biomarker analyses, including additional sensitivity analyses, will be outlined in the specific statistical analysis plan/summary.

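### The secondary biomarker-outcome tests are each judged at an unadjusted two-sided 5%, while other sections call the biomarker work exploratory; the status of these tests should be settled before analysis.

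*SAP*

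**What the plan says.** SAP 2.2 lists among the secondary objectives correlating germline BRCA1/2 methylation, and BRCA1/2 expression, with efficacy. SAP 9.2.3 (same content in Protocol 8.2.8) assigns the methods: univariate Cox models for PFS and OS, and chi-square or ANOVA for the efficacy rates.

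The level comes from the general sections. SAP 9.1: "A bilateral (2-sided) 5% significance level will be used to assess the statistical significance". SAP 9.2: "All statistical tests will be performed with a significance level of 5%, unless otherwise specified". Nothing in 9.2.3 specifies otherwise, and neither document contains a testing order, an alpha split or an adjustment.

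Markers and forms:
- Methylation: both "promoters will be measured in germline DNA from blood cells collected at the beginning of the study". It is supplied as a continuous value "and also as a binomial variable (status methylated or not methylated").
- Expression: BRCA1 and BRCA2 mRNA "will be assessed in blood and available tumour samples". On its form: "Expression data will be given as a continuous or as a binomial variable". No expression cut-off is given.

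Against this, SAP 9.2.4.1 says: "The biomarker analyses of the present study will be exploratory and primarily make use of descriptive statistical methods". Protocol 6.3.4 likewise says that relations between centrally assessed biomarkers and olaparib sensitivity or resistance are reported in an exploratory way.

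**The concern.** Read literally, any p<0.05 among the 9.2.3 tests is statistically significant under SAP 9.1 and 9.2 and belongs to a declared secondary objective. Read through 9.2.4.1, the same result is an exploratory observation. The plan does not say which reading governs.

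The number of tests makes this matter. No gene, tissue or endpoint is named as the one that counts. Methylation may be tested in two forms, and the form for expression is left open, so it could be chosen after outcomes are known. With about 31 patients, a chance association of methylation or expression with response or survival is quite likely, and the present wording would let it be reported as a significant secondary finding.

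**Working it through.** The documents state neither a test count nor a family-wise error rate, so there is no plan figure to reproduce. The count below is a reconstruction.

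**Inputs from the documents**
- Level: two-sided 0.05 per test (SAP 9.1, 9.2).
- Markers: germline methylation of BRCA1 and BRCA2 (2); mRNA of BRCA1 and BRCA2 in blood and in tumour (4). That is 6 if the genes are tested separately, or 3 if BRCA1/2 is one combined marker. SAP 9.2.3 does not say which.
- Outcomes: objective response and clinical benefit (SAP 9.2), PFS and OS (SAP 9.2.3), so 4.
- Sample size: 31 evaluable patients (SAP 3.1).

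**Number of tests**
- Combined marker, one form: 3 x 4 = 12.
- Separate genes, one form: 6 x 4 = 24.
- Separate genes, methylation in both forms, expression in one: (2 x 2 + 4) x 4 = 32.

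Not counted: duration of response, repeats in the ITT population, and the tests of change and concordance in 9.2.3 (pre/post treatment, germline/somatic, primary/metastatic, expression/methylation).

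**Chance of at least one p<0.05 when no marker is associated with any outcome**

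Independent tests, 1 - 0.95^m:
- m = 12: 1 - 0.540 = 46%
- m = 24: 1 - 0.292 = 71%
- m = 32: 1 - 0.194 = 81%

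The expected number of false positives is 0.05 x m whatever the correlation: 0.6, 1.2 and 1.6.

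The tests are not independent, because the markers and the outcomes are each related. Two checks allow for this. The correlations are assumptions; the documents give none.

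1. *Simulation.* n = 31, 1,500 runs per scenario, marker correlation 0 to 0.7, outcome correlation 0.6 to 0.8. It also assumed a response rate of 30%, a clinical benefit rate of 40%, censored survival times and complete data on every marker. Continuous markers were tested by two-group comparison for the rates and univariate Cox for PFS and OS.
   - 12 tests: about 31-39%.
   - 24 tests: about 40-62%, with on average 1.2 to 1.4 false positives.
   - 24 tests in binary form (Fisher's exact test and Cox): about 41-53%.
   - With all correlations set to zero, 12 and 24 continuous-form tests gave 44% and 69%, close to the 46% and 71% above.

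2. *Equal correlation rho between all test statistics.* The chance is 1 - E[{Phi((1.96 - sqrt(rho)U)/sqrt(1 - rho)) - Phi((-1.96 - sqrt(rho)U)/sqrt(1 - rho))}^m], with U standard normal.
   - m = 24: 46% at rho = 0.5; 24% at rho = 0.8.
   - m = 12: 32% at rho = 0.5; 19% at rho = 0.8.

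No simulation was run for exactly 32 tests.

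**The case against.** The best reply is that the plan already limits these analyses. SAP 9.2.4.1 speaks of the study's biomarker analyses in general. Protocol 6.3.4 covers samples for both secondary and exploratory objectives and uses exploratory language. Protocol 6.3.2 says that any relation between tumour methylation and response would need later studies. SAP 8 and the note to the SAP 10 table list make these outputs depend on available patients and samples. Odds ratios and hazard ratios with 95% confidence intervals are already planned (SAP 9.1, 9.2). The plan states 5% per test and never promises 5% across a family, and unadjusted biomarker correlations are common in small single-arm phase II trials.

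Most of this stands, and it makes the problem one of reporting and interpretation. It does not remove the conflict. SAP 9.2.4.1 sits under the exploratory analyses, while SAP 2.2 against 2.3, 9.2.3 against 9.2.4.1, and table block 4 against block 5 keep the secondary biomarker work apart. If 9.2.4.1 does cover 9.2.3, the 5% rule in 9.1 and 9.2 contradicts it. Either way the text needs the same edit.

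A reader might infer more than the documents support:
- That 24 is a minimum, or that 48 tests are planned. Combining the genes gives 12. Forty-eight needs expression in both forms, and the SAP offers one or the other.
- That a stated family-wise guarantee is breached. None is stated.
- That the risk is a false predictor of olaparib benefit. A single arm cannot show prediction of benefit at any alpha level.
- That "All of the above secondary analyses will be conducted at a two-sided 0.05 level of significance" in SAP 9.2.1.2 governs the biomarker tests. It refers to clinical benefit, duration of response, PFS and OS, and is a separate matter.

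**Conclusion.** The point holds as an inconsistency with a material but uncertain size. Secondary biomarker-outcome tests are prescribed at an unadjusted two-sided 5%, with no hierarchy, while other text treats biomarker analyses as exploratory. If every null hypothesis is true, the chance of at least one nominally significant association is about 31-39% (12 tests) to 40-62% (24 tests) in simulation. It is 46% and 71% under independence, and falls to 19% and 24% at a uniform correlation of 0.8. Every reading examined is well above 5%.

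These figures rest on a reconstructed count, assumed correlations, complete marker data and a global null. They support no single headline probability. The primary ORR rule of at least 14 responders is untouched. This is a cheap improvement to what may be concluded from an isolated p-value; it does not threaten the trial's main result.

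**What to change.** In SAP 9.2.3 and Protocol 8.2.8:
1. State that the biomarker-outcome analyses are hypothesis-generating and exempt from the 5% significance rule of SAP 9.1 and 9.2, and report effect estimates with 95% confidence intervals. This also brings 9.2.3 into line with SAP 9.2.4.1 and Protocol 6.3.4.
2. Make the continuous value the analysis form for methylation and mRNA, with the binary form as descriptive display only.
3. List the marker-by-endpoint tests, saying whether BRCA1 and BRCA2 are separate. If p-values are shown, report the number of tests run and add Benjamini-Hochberg adjusted values across that list.

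Cost: wording in both documents and one extra column in SAP tables 4.2 and 4.5. No new data or patients are needed. The downside is that an isolated nominal p<0.05 can no longer be called significant.
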